5.3 Summary of study visits

5.3.1 Screening visit

Informed consent must be obtained within the 28 days prior to administration of the first dose of study drug.

Patients must provide written informed consent before any screening-specific assessments are performed. Study centers must maintain a log of all consenting patients, which must include date and time of consent.

Screening assessments must be performed in accordance with Table 8 or Table 9. Screening must be initiated and completed within the 15 days prior to Day 1 of Phase 1 Cycle 1 (except for certain radiology assessments, which may be obtained within the 35 days prior to Day 1).

Patients will be assigned a subject number once they have provided consent. Patients are considered to be enrolled in the study once it is confirmed that they meet all of the eligibility criteria for the study.

Abnormal findings from the physical examination must be recorded (see Section 5.5.3). Body weight and height must also be recorded.

Vital signs and ECG must be performed as described in Sections 5.5.4 and 5.5.5.

BP measurements should be obtained as described in Section 5.5.4.3 and Table 10.

Transthoracic echocardiography must be performed as described in Section 5.5.6.

Laboratory safety tests (hematology, biochemistry, coagulation, cardiac troponin and urinalysis) must be assessed as described in Section 5.5.7.

Women of child-bearing potential must have a negative serum pregnancy test (hCG) conducted at screening, as described in Section 5.5.7.6 (see also Section 7.3).

Procedures for obtaining and handling blood samples and archival tumor specimens are described in Sections 5.8.1 and 5.8.3, respectively. If a tumor biopsy is taken in Phase 1 (if easily accessible and deemed safe for the patient by the Investigator and if patients are willing to undergo biopsy, see Section 5.8.1.1), the blood samples for biomarker analysis should be obtained prior to tumor biopsy.

The assessment of cancer and the selection and reporting of radiological marker lesions or other assessment endpoints (CA-125 or PSA) are described in Section 5.6.

A chest X-ray (or chest CT scan) must be performed in patients in the Phase 1 portion of the study to establish a baseline for safety assessments and will be repeated as clinically indicated. For tumor assessments, a chest CT scan should be performed. When a chest-CT scan is performed, a chest X-ray is not required (see Section 5.6).

Available radiology assessments conducted for solid-tumor patients within the 35 days prior to Day 1 of Phase 1 Cycle 1, or for GBM/high-grade glioma patients within the 15 days prior to Day 1 of Cycle 1, do not need to be repeated during Screening.

5.3.2 Day 1 to Day 28 of the Phase 1 and Phase 2a

BAL101553 capsules will be given to fasted patients daily (q24h or q12h, see Sections 3.2.1 and 3.2.4), continuously, until disease progression, unacceptable toxicity or another reason for withdrawal from study drug occurs (see Section 4.4). Each patient will be scheduled to receive at least two 28-day treatment cycles; there will be no treatment-free interval between treatment cycles.

Prior to first drug administration, patients will be counselled on how to take BAL101553 and how to fill in information in their drug diary, which will be provided (see Section 6.5). BAL101553 capsules in bottles will be dispensed to patients at each study visit. Patients will be instructed to return all bottles, including any unused drug, at the next visit. Drug accountability will be performed and assessed according to the drug diary entries and the number of capsules returned at each study visit (see Sections 6.5 and 6.6); patients will be counselled on compliance as is appropriate.

5.3.2.1 Day 1 of Cycle 1 and Cycle 2

Eligible patients enrolled in the study will return to clinic on study Day 1. Assessments on Day 1 of Cycle 1 and Cycle 2 will be performed in accordance with Table 8, or Table 9 for patients in the Phase 2a portion of the study.

On the day of drug administration, all patients must have fasted for at least 4 h (see Section 3.1.4 for more details).

Abnormal findings and clinically significant changes from screening apparent from the physical examination will be recorded. The findings from the physical examination on Day 1 of Cycle 1, before the first administration of BAL101553, will be regarded as baseline result.

Complete vital signs, and ECG will be performed at intervals corresponding to selected PK blood sampling time points, as described in Sections 5.5.4 and 5.5.5.

BP measurements should be obtained pre-dose and post-dose, as described in Section 5.5.4 and Table 10.

On Day 1 of Cycle 1, safety laboratory tests for hematology, biochemistry, cardiac troponin, coagulation and urinalysis (see Section 5.5.7.1) do not need to be repeated if conducted during screening within the 72 h prior to BAL101553 dosing.

Pregnancy testing (hCG) must be conducted for women of child-bearing potential, as described in Section 5.5.7.6.

Blood samples for PK analysis will be collected at serial time-points, as described in Section 5.7.1. 24-h urine sampling will be performed in solid-tumor patients during the Phase 1 portion of the trial for analysis of drug and drug metabolite excretion (see Section 5.7.2). Urine PK samples will not be taken from GBM/high-grade glioma patients.

Blood samples for biomarker analysis will be obtained on Day 1 of Cycle 1 as described in Section 5.8.1.

5.3.2.2 Day 8, Day 15, Day 22 and Day 28 of Cycle 1 and Cycle 2

Patients will return to the clinic and assessments will be performed in accordance with Table 8, or Table 9 for patients in the Phase 2a portion of the study. Day 28 assessments of a given cycle may be performed on Day 29 of that cycle, i.e., pre-dose on Day 1 of the subsequent cycle.

On the day of drug administration, all patients must have fasted for at least 4 h (see Section 3.1.4 for more details).

Vital signs will be performed pre-dose and post-dose as described in Section 5.5.4; ECG will be performed pre-dose and post-dose as described in Section 5.5.5.

BP measurements should be obtained pre-dose and post-dose, as described in Section 5.5.4 and Table 10.

Laboratory safety tests (hematology, biochemistry and cardiac troponin) will be assessed as described in Section 5.5.7.

Blood samples for pharmacokinetic (PK) analysis will be collected pre-dose on Day 8, Day 15 and Day 22 of Cycles 1 (both Phases) and 2 (Phase 1), as described in Section 5.7.1.

Blood samples for biomarker analysis in Phase 1 will be obtained pre-dose on Day 8, Day 15 and Day 22 of Cycle 1; and Day 22 Cycle 2; as described in Section 5.8.1.1.

In Phase 1, tumor biopsies will be obtained on Day 22 of Cycle 1 and/ Cycle 2, if easily accessible and deemed safe for the patient by the Investigator, and if the patient is willing to undergo biopsy (see Section 5.8.1.2).

Patients with measurable tumors will undergo radiological assessment of the tumor between Days 15 and 28 of Cycle 2. Efficacy assessments for patients with non-measurable ovarian or prostate cancer will be performed between Days 22 and 28 of all cycles. The assessment of cancer and the selection and reporting of radiological marker lesions or other assessment endpoints (CA-125 or PSA) are described in Section 5.6.

If efficacy evaluations on Day 28 of Cycle 2 demonstrate absence of disease progression, patients may be eligible to continue treatment with BAL101553.

5.3.2.3 Day 1 of subsequent treatment cycles

Patients eligible to continue treatment will return to clinic, and assessments on Day 1 of subsequent cycles will be performed in accordance with Table 8, or Table 9 for patients in the Phase 2a portion of the study.

On the day of drug administration, all patients must have fasted for at least 4 h (see Section 3.1.4 for more details).

Abnormal findings and clinically significant changes from baseline (Day 1 of Cycle 1) apparent from the physical examination will be recorded.

Vital signs will be performed pre-dose and and post-dose as described in Section 5.5.4. ECG will be performed pre-dose as described in Section 5.5.5.

BP measurements should be obtained pre-dose and post-dose, as described in Section 5.5.4 and Table 10.

Laboratory safety tests (hematology, biochemistry, coagulation and urinalysis) will be assessed as described in Section 5.5.7.

In Phase 2a, a liquid biopsy for biomarker research should be obtained after the confirmatory MRI scan for complete response/partial response (see Section 5.8.1

Pregnancy testing must be conducted for women of child-bearing potential, as described in Section 5.5.7.6.

5.3.2.4 Day 15 and Day 28 of subsequent treatment cycles

Patient will return to clinic and assessments will be performed in accordance with Table 8, or Table 9 for patients in the Phase 2a portion of the study.

Day 28 assessments of a given cycle may be performed on Day 29 of that cycle, i.e., predose on Day 1 of the subsequent cycle.

On the day of drug administration, all patients must have fasted for at least 4 h (see Section 3.1.4 for more details).

Vital signs will be performed pre-dose and post-dose as described in Section 5.5.4.

BP measurements should be obtained pre-dose and post-dose, as described in Section 5.5.4 and Table 10.

Laboratory safety tests (hematology and biochemistry) will be assessed on Day 15 as described in Section 5.5.7.

Where possible in Phase 1, post-treatment tumor biopsies (see Section 5.8.1.2) may be obtained on Day 22 of one subsequent cycle after Cycle 2, or at progressive disease.

Patients with measurable tumors will undergo radiological assessment of the tumor during the last two weeks (Day 15 to Day 28) of all even numbered cycles. From Cycle 6 onwards, the interval between CT/MRI scans may be extended from 8 weeks to 12 weeks. Efficacy assessments for patients with non-measurable ovarian or prostate cancer will be performed during the last week (Day 22 to Day 28) of all cycles. The assessment of cancer and the selection and reporting of radiological marker lesions or other assessment endpoints (CA-125 or PSA) are described in Section 5.6.

After treatment for more than 12 cycles, D15 visits may be skipped in patients with an adequate and stable condition as per Investigator's clinical judgement.

5.3.3 End of Study visit

End of Study assessments are to be performed in patients who no longer receive BAL101553 treatment, and must take place within 7 days after the decision to discontinue treatment. Assessment will be performed in accordance with Table 8, or Table 9 for patients in the Phase 2a portion of the study.

Abnormal findings and clinically significant changes from baseline (Day 1 of Cycle 1) apparent from the physical examination will be recorded.

Vital signs (including BP) will be performed as described in Section 5.5.4. An ECG will be performed, as described in Section 5.5.5.

Transthoracal echocardiography will be performed as described in Section 5.5.6.

Laboratory safety tests (hematology, biochemistry, coagulation, cardiac troponin and urinalysis) will be assessed as described in Section 5.5.7.

Pregnancy testing must be conducted for women of child-bearing potential (see Section 5.5.7.6).

A blood sample for PK analysis will be collected, as described in Section 5.7.1.

In Phase 2a, a liquid biopsy for biomarker research should be obtained (see Section 5.8.1.2).

Radiology efficacy assessments must be repeated, if these have not been performed within the 35 days prior to the End of Study visit. Assessment of CA-125 or PSA in patients with non-measurable ovarian or prostate cancer must be repeated if these have not been performed within the 14 days prior to the End of Study visit. The assessment of cancer and the selection and reporting of radiological marker lesions or other assessment endpoints (CA-125 or PSA) are described in Section 5.6.

5.3.4 Follow-up contact

Assessment of vital status and AE monitoring must be continued for at least 28 days following the last dose of study treatment. Patients must also be contacted to record antineoplastic therapies received after discontinuation of study drug. All cancer medications/therapies given to the patient \leq 28 days after the last dose of study drug must be recorded in the CRF.

Follow-up information can be obtained during an in-clinic visit, or by telephone if no physical assessments are required. Patients exhibiting abnormalities or reporting AEs at the time of follow-up contact must be followed (see Sections 7.2.5 and 7.2.6).

5.3.5 Overall survival follow-up

Survival follow-up in the Phase 2a portion will start the day of the last dose of study drug. All patients and/or family will be contacted at 3-month intervals (±14 days), with the patient status to be recorded as *Alive* (date); *Dead* (date); *Alive*, *but withdrew consent for further follow up* (last date under consent); or *Lost to Follow Up* (date of last contact). Survival updates may be made more often than every 3 months if the patient is seen at the investigational site for other reasons, and for overall study status assessments. The survival follow-up period will continue until the study has been completed (see Section 9.5), or other discontinuation criteria are met (see Section 4.4).

Note: Survival follow-up can be done either over the telephone, or by collection of public records in accordance with local laws.

5.4 Medical history, prior and concomitant medications

A full medical history must be obtained at Screening.

All prior medications taken within 30 days of the Screening visit must be documented for each patient in the CRF. Any medications or significant non-drug therapies (including herbal medicines) that are taken by or administered to the patient during the course of the study (until the End of Study visit) must be recorded in the CRF including the dosage, dose regimen, route of administration, therapeutic indication, and start/stop dates of use.

All prior anti-cancer treatments, including cancer surgeries, radiation therapy and chemotherapy/ medications since the diagnosis of cancer must be assessed during screening and documented for each patient in the CRF.

All non-antineoplastic medications which were received by the patient within 4 weeks prior to screening must also be recorded in the CRF.

5.4.1 Concomitant medications not permitted during the study

In general, the use of concomitant medications or treatments considered necessary for appropriate patient care is permitted during the study with the following exceptions:

- Other investigational therapies must not be used while the patient is included in the study.
- Anticancer therapy (including cancer surgery, chemotherapy, biological or radiation therapy) other than BAL101553 must not be given while the patient is included in the study. After completion of Cycle 1, single-fraction palliative radiotherapy is permitted if the respective tumor lesion is not the only index lesion, and if criteria of disease progression are not met. The concurrent use of OptuneTM is not permitted.
- If other anticancer therapy is required for a patient then this patient must be discontinued from the study.
- Coumarin derivates (including warfarin potassium, phenprocoumon or acenocoumarol) are not permitted. Other anticoagulant treatments (including heparin, low-molecular weight heparin, direct thrombin/factor Xa inhibitors, aspirin, or other oral platelet inhibitors such as clopidogrel) are allowed.
- New medications should be avoided on the days of full PK sampling, if medically feasible.

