5.6 Efficacy assessments

At Screening, patients with advanced or recurrent solid tumors must have measurable disease (according to RECIST criteria v1.1), or non-measurable disease that can be followed by an acceptable tumor marker (CA-125 or PSA), prior to initiation of study treatment.

Patients with recurrent or progressive glioblastoma or high-grade glioma must be evaluated according to RANO criteria.

All radiological tests that demonstrated tumor at baseline (i.e., at Screening, or within 35 days prior to starting study drug for patients with advanced or recurrent solid tumors or within 15 days prior to starting study drug in patients with recurrent or progressive glioblastoma or high-grade glioma) must be repeated within 1 (Phase 1) or 2 (Phase 2a) weeks of completion of every even numbered cycle prior to the next administration of BAL101553. From Cycle 6 onwards, the interval between CT/MRI scans may be extended from 8 weeks to 12 weeks. Each lesion measured at baseline is to be measured throughout the study by the same method of assessment and the same technique (e.g., consistent use of CT with same anatomic coverage, contrast administration (unless medically contraindicated), slice thickness, and reconstruction interval at all time points) in order to allow for consistent assessments and comparisons. To determine complete response or partial response the required criteria must be present for at least 4 weeks.

Patients with objective response or stable disease will be permitted to continue to receive additional cycles of BAL101553 until disease progression or unacceptable toxicity. No patients are permitted to start subsequent cycles if unequivocal progression is observed, concerning mixed response see Section 4.4.

At study treatment completion (End of Study visit), radiology efficacy assessments must be repeated if these have not been performed within 35 days prior to this day. Assessment of CA-125 or PSA in patients with non-measurable ovarian or prostate cancer must be repeated if these have not been performed within 14 days prior to this day.

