Appendix 6 RANO criteria for glioblastoma and high-grade gliomas

Source

Criteria for Response Assessment Incorporating MRI and Clinical Factors

Response	Criteria
Complete response	Requires all of the following: complete disappearance of all enhancing measurable and nonmeasurable disease sustained for at least 4 weeks; no new lesions; stable or improved nonenhancing (T2/FLAIR) lesions; patients must be off corticosteroids (or on physiologic replacement doses only); and stable or improved clinically. Note: Patients with nonmeasurable disease only cannot have a complete response; the best response possible is stable disease.
Partial response	Requires all of the following: \geq 50% decrease compared with baseline in the sum of products of perpendicular diameters of all measurable enhancing lesions sustained for at least 4 weeks; no progression of nonmeasurable disease; no new lesions; stable or improved nonenhancing (T2/FLAIR) lesions on same or lower dose of corticosteroids compared with baseline scan; the corticosteroid dose at the time of the scan evaluation should be no greater than the dose at time of baseline scan; and stable or improved clinically. Note: Patients with nonmeasurable disease only cannot have a partial response; the best response possible is stable disease.
Stable disease	Requires all of the following: does not qualify for complete response, partial response, or progression; stable nonenhancing (T2/FLAIR) lesions on same or lower dose of corticosteroids compared with baseline scan. In the event that the corticosteroid dose was increased for new symptoms and signs without confirmation of disease progression on neuroimaging, and subsequent follow-up imaging shows that this increase in corticosteroids was required because of disease progression, the last scan considered to show stable disease will be the scan obtained when the corticosteroid dose was equivalent to the baseline dose.

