4.5 Pharmacokinetic analysis population(PK)

The PK analysis set includes all patients who received at least one dose of study drug and had at least one post-baseline PK assessment.

4.6 Efficacy-evaluable population (Phase 2a expansion portion of the study, Simon's two-stage design)

The efficacy evaluable population (EEP) is the subset of the FAP who had at least one post baseline RANO assessment after having received at least 6 weeks of study treatment.

For objective response rate and stage transition, the analysis will be based on patients with measurable disease at baseline in the EEP.

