5 STATISTICAL CONSIDERATIONS AND ANALYSIS

5.1 Derived variables

The following derived variables will be applied throughout the study:

- Baseline is defined as the last available assessment prior to first dose intake (including unscheduled assessments), e.g. Cycle 1 Day 1 pre-dose.
- Last/Final for safety is the first available value after treatment or, if not available, then immediately before last treatment.
- Adverse event (AE) duration (in days) will be calculated as (the times will not be considered): Event end date - Event onset date + 1.
- The following algorithm will be used for the study day determination:
 - Day 1 = Day of first study drug administration (i.e. at Cycle 1 Day 1). The day before day 1 is day-1.
 - Prior to Day 1 the algorithm is (<visit/examination date> minus <date of first study drug administration >)
 - Day 1 and subsequent days = (<visit/examination date> minus <date of first study drug administration >) + 1.
- Duration of exposure (in days) will be calculated as: Date of last study drug administration – Date of first study drug administration + 1.
- The response according to RECIST or RANO criteria will be as reported in the Case report form (CRF).

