6.2 Efficacy analysis

6.2.1 Objective response rate

The objective response rate will be calculated within the FAP (Phase 1 portion of the study), as the proportion of patients responding (i.e., with a best observed objective response of complete response (CR) or partial response (PR), based on RECIST criteria v1.1 for patients with advanced or recurrent solid tumors); and based on RANO criteria for patients with recurrent or progressive GBM/high-grade glioma.

In the Phase 2a portion of the study (Simon's two-stage design), the patients with measurable disease at baseline in the EEP will be the primary population for the calculation of the objective response rate.

A patient who has a response unknown or not reported will be treated as non-responder.

The proportion and its exact 95% confidence interval (CI) will be presented by disease subgroup and by dose cohort.

Waterfall plots, spider plots and swimmer plot summarizing tumor size, best response and treatment duration will also be provided.

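### Minor and cheap to close: no supplied text keeps a Phase 2a response that follows permitted radiotherapy to an index lesion out of the 6-of-19 count

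*Protocol*

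**What the plan says.** **Permission.** Protocol 5.4.1 prohibits other anticancer therapy on study. The exception starts once Cycle 1 is complete: "single-fraction palliative radiotherapy is permitted if the respective tumor lesion is not the only index lesion", as long as progression criteria are not met. It names no phase. Section 4.4 makes a need for other anticancer therapy a reason to stop treatment. It does not mention this exception and does not say how a response is scored.

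**Measurement.** Protocol 5.6: "Each lesion measured at baseline is to be measured throughout the study by the same method of assessment". Protocol 5.3.2.2: "Patients with measurable tumors will undergo radiological assessment of the tumor between Days 15 and 28 of Cycle 2". Appendix 6 defines partial response as a fall of at least 50% in the "sum of products of perpendicular diameters of all measurable enhancing lesions sustained for at least 4 weeks", and 5.6 repeats the duration: "To determine complete response or partial response the required criteria must be present for at least 4 weeks". Irradiated lesions are not set apart. Radiation appears in Appendix 6 only among the alternative explanations for a T2/FLAIR increase.

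**Counting.** SAP 5.1 takes the RANO response as entered in the CRF. SAP 6.2.1 converts one kind of record to a non-response: "A patient who has a response unknown or not reported will be treated as non-responder". SAP 4.6 applies the same responses at the interim look: "For objective response rate and stage transition, the analysis will be based on patients with measurable disease at baseline in the EEP".

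**Decision rule.** Protocol 8.3.3.2 and SAP 3.3.3: stop at 1 or fewer responses in 9, otherwise continue to 19, and reject a 14% response rate at 6 or more. The stated type I error is 3.7%, with 81% power at 40%.

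**The concern.** In a single-arm test every counted response is attributed to the drug. If a patient with two or more index lesions has the larger one irradiated, the summed area can halve without any drug effect. Followed as written, the plan scores that patient as a responder, both at the Stage 1 gate and in the final count. Since 5 versus 6 responders decides the test, one such patient can settle it.

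The plan also leaves the counting choice open. Anyone who wished to exclude such a patient would have to decide after the response was known, in an open-label study.

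**Working it through.** **1. The stated figures.** Inputs are from Protocol 8.3.3.2. With X1 ~ Bin(9, p) and X2 ~ Bin(10, p), P(reject) = sum over x = 2 to 9 of P(X1 = x) × P(X2 ≥ 6 − x).

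- p = 0.14: P(pass Stage 1) = 0.3657, P(reject) = 0.0371.
- p = 0.40: P(reject) = 0.8132.

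Both stated figures reproduce.

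**2. Timing.** Cycles last 28 days, so radiotherapy is possible from Day 29. Days 15 to 28 of Cycle 2 are study Days 43 to 56. Radiotherapy can therefore precede the first response MRI by up to 43 − 29 = 14 to 56 − 29 = 27 days.

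**3. What the irradiated lesion must do.** Let it hold share s of the baseline sum, with the other lesions unchanged. A 50% fall in the sum needs a fall of 0.5/s in that lesion: 100% at s = 50%, 71% at 70%, 63% at 80%. Below a 50% share it cannot produce a partial response alone.

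**4. Illustrative effect on type I error.** The documents give no rate of on-study radiotherapy or of conversion to response, so this is assumption. Let q = (share of null non-responders irradiated) × (share of those converted to CR/PR). The counted rate becomes p' = p0 + (1 − p0)q. The chance of at least one such patient among 19 is 1 − (1 − (1 − p0)q)^19.

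| q (example) | p' at p0 = 14% | P(at least one in 19) | P(pass Stage 1) | Type I error at 14% | Rejection probability at true 8% |
|---|---|---|---|---|---|
| 0 | 14.00% | 0 | 36.6% | 3.7% | 0.26% |
| 0.1% (2% × 5%) | 14.09% | 1.6% | 36.9% | 3.8% | 0.28% |
| 0.5% (5% × 10%) | 14.43% | 7.9% | 38.1% | 4.2% | 0.35% |
| 1% (10% × 10%) | 14.86% | 15% | 39.6% | 4.8% | 0.45% |
| 2% (10% × 20%) | 15.72% | 28% | 42.5% | 6.0% | 0.73% |

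At a true 3% rate the rejection probability is at most 0.02% over the same range. The 3%, 8% and 14% rates are the historical values in Protocol 1.5.2.2.1.

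**5. Cost of a rule that does not count such responses.** If a share l of genuine responders is lost, the counted rate is p(1 − l).

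| l (assumption) | Power at 40% | Type I error at 14% |
|---|---|---|
| 0 | 81.3% | 3.7% |
| 1% | 80.4% | 3.6% |
| 2% | 79.4% | 3.4% |
| 5% | 76.4% | 3.0% |

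If no radiotherapy-driven response is counted, the counted rate cannot exceed the true drug rate. Type I error at a true 14% then stays at or below 3.7%.

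**The case against.** **Other rules close most of the route.** The exception requires that progression criteria are not met. Protocol 5.6.3 treats signs and symptoms of clinical progression as progressive disease, and Appendix 6 adds clinical deterioration, new lesions and T2/FLAIR increase. A patient who needs palliation of a brain lesion will often fall outside the exception. What is left needs several index lesions, a dominant irradiated one, stable or better clinical status and T2/FLAIR, no steroid increase, and 4 weeks' persistence. This stands, and it is why the point is minor.

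**The exception may be a carry-over from the solid-tumor part.** Single-fraction palliative radiotherapy otherwise appears only in the solid-tumor paragraph of exclusion criterion 1, and index lesion is not an Appendix 6 term. This is plausible, but the text as written applies to Phase 2a. The protocol names the phase elsewhere when it means to limit a rule, as with the radiotherapy washout in that same criterion.

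**The RANO guidelines may deal with locally treated lesions.** Protocol 5.6.1.2 refers to them, and only Appendix 6 is supplied. A reader might infer that RANO itself has no rule. The documents cannot show that, so the gap is established for the supplied text alone.

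**The case would be visible.** Protocol 5.4 puts non-drug therapies and their dates in the CRF, and SAP 6.3.8 lists them by patient. A reader could recount. This stands, but a listing does not say which count is primary.

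**A remedy discards real responses.** It does so even where untreated lesions also shrank. At a 0.1% contamination rate the type I error saved is about 0.1 percentage point, against 0.9 point of power if 1% of responders are lost. This also stands, and a sensitivity analysis that counts the response as reported is the answer to it.

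**Conclusion.** The gap is real but small. Protocol 5.4.1, Appendix 6, SAP 5.1 and SAP 6.2.1 together would count a radiotherapy-driven CR/PR toward the drug, and no supplied passage prevents it at stage transition or in the final test.

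A reader might infer that the 3.7% is wrong or that the 6-of-19 test is compromised. The documents do not support either. The stated figures are exact for the stated rule. The 3.8% to 6.0% range rests on assumed rates, and its upper end (q = 2%, a 28% chance of at least one such patient in 19) sits badly with a case that is probably rare. The effect is negligible at a true 8% or 3% rate. A reader might also take the result for one certain radiotherapy-driven response among the 19 as the trial's error rate: 9.4% if it falls in Stage 1 and 8.5% if in Stage 2, at a true 14%. Those figures are conditional on the event happening.

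The case for acting is that the counting rule costs little to fix now and would otherwise be argued after the response is known.

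**What to change.** In Protocol 8.3.2.5 and SAP 6.2.1, add for the Phase 2a objective response rate and stage-transition count only:

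> A CR/PR first documented after on-study radiotherapy to a measurable enhancing lesion, or not confirmed at 4 weeks before it, is counted as a non-response. The patient stays in the EEP and the denominator and is not replaced. Such patients are listed, and a sensitivity analysis counts the response as reported.

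State as well that EEP membership and the disease control rate continue to use all RANO assessments. SAP 6.2.2 builds disease control on best response. A rule that limited which scans feed best response could therefore strip a stable patient irradiated before the first MRI of disease-control status, and might make that patient look non-evaluable under Protocol 4.5.

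The permission to give radiotherapy need not change, and no extra scan is required. The cost is a few sentences, one listing and one sensitivity analysis, using therapy dates already collected under Protocol 5.4.

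The downside is that a genuine drug response first seen or confirmed after radiotherapy is lost. The next scheduled MRI (Cycle 4, study Days 99 to 112) falls 99 − 56 = 43 to 112 − 43 = 69 days after the first, so radiotherapy given between the two can forfeit a response seen at the first. If 1% or 2% of true responders were affected (assumption), power would fall from 81.3% to 80.4% or 79.4%.
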